7.5.3. Severity of an Adverse Event

The severity of each adverse event must be recorded as 1 of the choices on the following scale:

- Mild:** No limitation of usual activities
- Moderate:** Some limitation of usual activities
- Severe:** Inability to carry out usual activities

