7.5.5. Serious Adverse Events

7.5.5.1. Definition of a Serious Adverse Event

A serious adverse event is an adverse event occurring at any dose that results in any of the following outcomes or actions:

- death
- a life-threatening adverse event (ie, the patient was at immediate risk of death from the event as it occurred); does not include an event that, had it occurred in a more severe form, might have caused death
- inpatient hospitalization or prolongation of existing hospitalization, which means that hospital inpatient admission or prolongation of hospital stay were required for treatment of an adverse event, or that they occurred as a consequence of the event

Hospitalizations scheduled before the patient signed the informed consent form will not be considered serious adverse events, unless there was worsening of the preexisting condition during the patient's participation in this study.

- Hospitalization for intravenous steroid treatment of a relapse will not be considered a serious adverse event unless it is a worsening of the condition beyond expected disease progression.
- persistent or significant disability or incapacity (refers to a substantial disruption of one's ability to conduct normal life functions)
- a congenital anomaly/birth defect
- an important medical event that may not result in death, be life-threatening, or require hospitalization, but may jeopardize the patient and may require medical intervention to prevent one of the outcomes listed in this definition
- Examples of such events are intensive treatment in an emergency room or at home for allergic bronchospasm; blood dyscrasias or convulsions that do not result in hospitalization; or the development of drug dependency or drug abuse. Note: Any suspected transmission of an infectious agent via a medicinal product is considered an important medical event.

All occurrences of possible drug-induced liver injury that meet Hy's law criteria, defined as **all** of the below, must be reported by the investigator to the sponsor as a serious adverse event:

- alanine aminotransferase (ALT) or aspartate aminotransferase (AST) elevation of >3x the upper limit of normal (ULN)
- total bilirubin elevation of >2x ULN
- absence of initial findings of cholestasis (ie, no substantial increase of alkaline phosphatase [ALP])

An adverse event that does not meet any of the criteria for seriousness listed above will be regarded as a nonserious adverse event.

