7.8. Laboratory Procedures

Blood samples and urine specimens must be obtained at the appropriate visits. Non-fasting samples may be obtained. Any laboratory samples which are outside the normal range must be assigned one of the following codes:

NS – Not Clinically Significant: A clinically meaningless departure from the normal range.

LE – Laboratory Error: Due to a poor sample, instrument error, etc. (the value is not valid).

PA – Patient Abnormality: Although the value is outside the normal range, the value is normal for that particular patient.

CS – Clinically Significant: A clinically meaningful departure from the normal range or a clinically meaningful change in the parameter. All clinically significant values during the study are adverse events and must be entered on the “Clinically Significant Lab Values” page of the Case Report Form.

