8.1. Adverse Events

The total number and percent of patients reporting adverse events, across and by body system and event term, will be tabulated for all patients treated. The number of patients treated will serve as the denominator for incidence rate computation. Adverse events will also be summarized by maximum reported severity and relationship to treatment. Detailed data displays, narrative summaries, and copies of Case Report Forms will be provided for those patients who withdrew prematurely due to an adverse event or who dies.

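### Laboratory adverse events fall under two unreconciled severity scales (Section 7.5.3 and Appendix F), neither uses the size of the value, and Section 8.2 does not recover it

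*Combined protocol and SAP*

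**What the plan says.** **Severity.** Section 7.5.3 is mandatory and has no laboratory exception: "The severity of each adverse event must be recorded as 1 of the choices on the following scale". The grades are mild ("No limitation of usual activities"), moderate ("Some limitation of usual activities") and severe ("Inability to carry out usual activities"). Section 7.5.2 has the investigator judge severity and record it by the sections that follow it.

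**Laboratory values as events.** Section 7.8 assigns each out-of-range result one of four codes. For the clinically significant code it says: "All clinically significant values during the study are adverse events". Section 7.5.1 likewise counts abnormalities that the investigator considers clinically significant.

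**A second scale.** Appendix F also defines mild, moderate and severe, and applies them expressly to laboratory as well as clinical events. Its definitions bring in how long the event lasts and what treatment it needs, alongside interference with daily life.

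**Analysis.** Section 8.1: "Adverse events will also be summarized by maximum reported severity and relationship to treatment". It does not separate clinical from laboratory events. Section 8.2 summarises each test at baseline, at the last value on treatment and as the change between them. It adds baseline-against-endpoint scatterplots and a count of clinically significant changes, under criteria left to the medical monitor.

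**The concern.** Clinical pathology is one of the two components listed under the long-term safety objective in Section 3. A reader of the severity table will take mild to mean a small problem. For a laboratory finding under Section 7.5.3, it means only that the patient's activities were not limited. If some sites grade by 7.5.3 and others by Appendix F, the table also mixes two meanings of each grade, and nothing in the output reveals which was used. A marked abnormality in a patient without symptoms could then sit in the mild row with nothing elsewhere in the planned tables to show its size.

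**Working it through.** No arithmetic applies to the definitions, and the plan gives no figure to reproduce. The check sets the scales side by side and runs test cases through them.

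**1. The two scales**

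| Grade | Section 7.5.3 | Appendix F (paraphrased) |
|---|---|---|
| Mild | "No limitation of usual activities" | Generally short-lived, no particular treatment needed, daily life undisturbed |
| Moderate | "Some limitation of usual activities" | Slight inconvenience or worry; disturbance of daily life is possible but not required; simple measures generally help |
| Severe | "Inability to carry out usual activities" | Breaks into daily life, and by custom calls for systemic or other therapy |

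Neither column mentions the laboratory value or its distance from the reference limit.

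**2. Test cases, all in patients with no activity limitation**

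| Case | Section 7.5.3 | Appendix F |
|---|---|---|
| Transient, untreated abnormality | Mild | Mild |
| Abnormality that persists or needs simple treatment | Mild | Does not fit mild; moderate is open |
| Extreme value needing systemic treatment | Mild | Does not fit mild; severe not clearly met, because daily life is not interrupted |

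As an illustration, take ALT at 3.1 times and at 20 times the upper limit of normal, both symptom-free, transient and untreated. They receive the same grade under Section 7.5.3, and the same grade under Appendix F.

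**3. Which scale governs.** Section 7.5.3 is worded as an obligation and Section 7.5.2 leads to it. Appendix F is part of the current protocol and is the only place that names laboratory events in connection with severity. In the text available, no current body section refers to Appendix F apart from the table of contents. No sentence says which scale prevails.

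**4. Effect on the Section 8.1 table.** Where the table is read by event term, a laboratory term such as a raised transaminase carries whatever grade the site's scale produced. In the second case above, that is mild or moderate for the same event. Where it is read across all of a patient's events, a clinical event of higher grade may mask the difference.

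**5. Whether Section 8.2 recovers the size.** Appendix A schedules laboratory draws at months 264, 276 and 288. Section 8.2 does not define baseline. Assume it is month 264 and the last value is month 288:

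- Baseline, last value and change use months 264 and 288 only.
- The minimum and maximum are taken across patients at those points. They are not each patient's own extreme over time.
- The scatterplots show the same two points per patient.
- The count of clinically significant changes might include month 276, but it carries no grade and its criteria are not stated.

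The size of a peak at month 276 that resolves by month 288 therefore appears in none of these displays. An earlier baseline would leave more intermediate values unseen. So would more frequent draws: Section 7.4 speaks of 6-month intervals.

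**6. Scale of exposure.** Section 3 gives about 60 patients. Three scheduled draws each give 60 × 3 = 180 panels at most on the schedule, before any unscheduled or early-termination draws. The documents do not say how many would yield a clinically significant value.

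**The case against.** **Appendix F.** A reader might infer from Section 7.5.3 that every symptom-free laboratory event is mild by rule, so that the severity table could never show one as moderate. The documents do not support that. Appendix F is current text, covers laboratory events, and leaves moderate open to a persistent or treated abnormality. The supported point is the conflict between the scales and their shared silence on magnitude.

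**Serious yet mild.** A reader might also see a contradiction in Section 7.5.5.1, which requires that "All occurrences of possible drug-induced liver injury that meet Hy's law criteria" be reported as serious, while 7.5.3 would grade a symptom-free case mild. It is not one. Sections 7.5.2 and 7.5.5.1 and Appendix F treat seriousness and severity as separate judgements. Dangerous laboratory patterns reach the sponsor through seriousness whatever the grade, and blood dyscrasias are named among the important medical events. This stands in full.

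**Section 8.2 already reports values.** In part it does. An extreme last value would be visible in the maximum and in the scatterplot. Section 8.1 adds narratives for deaths and for withdrawals due to adverse events. What remains unseen is the size of an intermediate peak in a patient who stays on study.

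**Low yield and low stakes.** Section 2.1 reports no clinically significant laboratory abnormalities associated with therapy over nearly 3 years of dosing. Values coded as not significant, laboratory error or normal for the patient do not become events under the Section 7.8 rule. The analyses are descriptive, and no test or stopping rule uses the grade. This limits the impact but does not remove the ambiguity.

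**Replacing judgement.** A derived grade should not displace the investigator's severity, and earlier results may not be held electronically with reference limits (electronic forms start at month 159, Section 9.5). Both points stand, and the fix allows for them.

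**Conclusion.** The point holds in this form. Under Section 7.5.3 a symptom-free laboratory adverse event fits only mild. Under Appendix F the same event may be moderate. Neither scale uses the size of the value. The Section 8.1 table therefore depends on the scale a site applied and can understate laboratory toxicity, and Section 8.2 does not show the size of an intermediate peak.

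The demonstrable discrepancy for one event is one grade, mild against moderate. The number of events affected is unknown, and no share of the severity table can be derived from the documents.

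The conclusion rests on three assumptions: Appendix F is still in force because it is still in the protocol; sites have no further grading instruction outside these documents; and Section 8.2 is carried out as written. The harm is to the interpretability of the safety summary, not to expedited reporting. It is worth correcting because the correction is cheap.

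**What to change.** 1. Reconcile Section 7.5.3 and Appendix F into one severity scale, stated once and cross-referenced, and say how it applies to laboratory adverse events.
2. Keep the severity recorded by the investigator as it is.
3. In Section 8.1, tabulate maximum severity separately for clinical and for laboratory adverse events.
4. In Section 8.2, add a programmed table of each patient's worst on-treatment value for the tests in Sections 7.8.2 and 7.8.3. Grade it by multiples of the reference limit or by one prespecified published laboratory grading. Restrict it to results held with reference limits, and state how many results are left out.

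**Cost.** Edits to Section 7.5.3, Appendix F and Section 8, and the programming of a derivation from results already collected. No new visit, sample or procedure is needed. Some laboratory events will look worse in the new table than in the site's grade. Since both are shown, the report should say that they measure different things. Tests without usable bands or reference limits stay ungraded. Serious adverse event reporting, including Hy's law, does not change.

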7.5.4. Relationship of an Adverse Event to the Study Drug

The relationship of an adverse event to the study drug is characterized as follows:

Term	Definition	Clarification
No reasonable possibility (not related)	This category applies to adverse events that, after careful consideration, are clearly due to extraneous causes (disease, environment, etc) or to adverse events that, after careful medical consideration at the time they are evaluated, are judged to be unrelated to the study drug.	
The relationship of an adverse event may be considered “no reasonable possibility” if it is clearly due to extraneous causes or if at least 2 of the following apply:
 
 • It does not follow a reasonable temporal sequence from the administration of the study drug. • It could readily have been produced by the patient’s clinical state, environmental or toxic factors, or other modes of therapy administered to the patient. • It does not follow a known pattern of response to the study drug. • It does not reappear or worsen when the study drug is re-administered.
Reasonable possibility (related)	This category applies to adverse events for which, after careful medical consideration at the time they are evaluated, a connection with the study drug administration cannot be ruled out with certainty.	
The relationship of an adverse event may be considered “reasonable possibility” if at least 2 of the following apply:
 
 • It follows a reasonable temporal sequence from administration of the study drug. • It cannot be reasonably explained by the known characteristics of the patient’s clinical state, environmental or toxic factors, or other modes of therapy administered to the patient. • It disappears or decreases on cessation or reduction in dose. There are important exceptions when an adverse event does not disappear after discontinuation of the study drug, yet a drug relationship clearly exists. • It follows a known pattern of response to the study drug.

7.5.5. Serious Adverse Events

7.5.5.1. Definition of a Serious Adverse Event

A serious adverse event is an adverse event occurring at any dose that results in any of the following outcomes or actions:

- death
- a life-threatening adverse event (ie, the patient was at immediate risk of death from the event as it occurred); does not include an event that, had it occurred in a more severe form, might have caused death
- inpatient hospitalization or prolongation of existing hospitalization, which means that hospital inpatient admission or prolongation of hospital stay were required for treatment of an adverse event, or that they occurred as a consequence of the event

Hospitalizations scheduled before the patient signed the informed consent form will not be considered serious adverse events, unless there was worsening of the preexisting condition during the patient's participation in this study.

- Hospitalization for intravenous steroid treatment of a relapse will not be considered a serious adverse event unless it is a worsening of the condition beyond expected disease progression.
- persistent or significant disability or incapacity (refers to a substantial disruption of one's ability to conduct normal life functions)
- a congenital anomaly/birth defect
- an important medical event that may not result in death, be life-threatening, or require hospitalization, but may jeopardize the patient and may require medical intervention to prevent one of the outcomes listed in this definition
- Examples of such events are intensive treatment in an emergency room or at home for allergic bronchospasm; blood dyscrasias or convulsions that do not result in hospitalization; or the development of drug dependency or drug abuse. Note: Any suspected transmission of an infectious agent via a medicinal product is considered an important medical event.

All occurrences of possible drug-induced liver injury that meet Hy's law criteria, defined as **all** of the below, must be reported by the investigator to the sponsor as a serious adverse event:

- alanine aminotransferase (ALT) or aspartate aminotransferase (AST) elevation of >3x the upper limit of normal (ULN)
- total bilirubin elevation of >2x ULN
- absence of initial findings of cholestasis (ie, no substantial increase of alkaline phosphatase [ALP])

An adverse event that does not meet any of the criteria for seriousness listed above will be regarded as a nonserious adverse event.

7.5.5.2. Expectedness

A serious adverse event that is not included in the Adverse Reaction section of the relevant reference safety information (RSI) by its specificity, severity, outcome, or frequency is considered an unexpected adverse event. The RSI for this study is the US prescribing information.

The sponsor's Global Patient Safety and Pharmacovigilance will determine the expectedness for all serious adverse events.

7.5.5.3. Reporting a Serious Adverse Event

7.5.5.3.1. Investigator Responsibility

To satisfy regulatory requirements, all serious adverse events (as described in Section 7.5.5.1) that occur during the study period (including the protocol-defined follow-up period, described in Section 7.5.2), regardless of judged relationship to treatment with the study drug, must be reported to the sponsor by the investigator. The event must be reported within 24 hours of when the investigator learns about it. Completing the serious adverse event form and reporting the event must not be delayed, even if not all the information is available. Any serious adverse event must be reported to the Teva Branded Pharmaceutical Products R&D, Inc., Local Safety Officer . Send by email using the Serious Adverse Event Form to the local safety officer (LSO). The email address will be provided in the serious adverse event report form. In the event of difficulty transmitting the form, contact the sponsor's study personnel for further instruction

The investigator does not need to actively monitor patients for adverse events once this study has ended. Serious adverse events occurring to a patient after the treatment of that patient has ended should be reported to the sponsor if the investigator becomes aware of them.

The serious adverse event form should be sent to the LSO . The LSO will forward the report to the sponsor's Global Patient Safety and Pharmacovigilance.

The following information should be provided to record the event accurately and completely:

- study number
- investigator and investigational center identification
- patient number
- onset date and detailed description of adverse event
- investigator's assessment of the relationship of the adverse event to the study drug (no reasonable possibility, reasonable possibility)

Additional information may include the following:

- age and sex of patient
- date of first dose of study drug
- date and amount of last administered dose of study drug
- action taken
- outcome, if known
- severity

- explanation of assessment of relatedness
- concomitant medication (including doses, routes of administration, and regimens) and treatment of the event
- pertinent laboratory or other diagnostic test data
- medical history
- results of dechallenge/rechallenge, if known
- for an adverse event resulting in death:
 - cause of death (whether or not the death was related to study drug)
 - autopsy findings (if available)

The investigator must ensure that the IEC/IRB is also informed of the event, in accordance with national and local regulations.

Each report of a serious adverse event will be reviewed and evaluated by the investigator and the sponsor to assess the nature of the event and the relationship of the event to the study drug, study procedures, and to underlying disease.

Additional information (follow-up) about any serious adverse event unavailable at the initial reporting should be forwarded by the investigator within 24 hours of when it becomes known to the same address as the initial report.

For all countries, the sponsor's Global Patient Safety and Pharmacovigilance will distribute the Council for International Organizations of Medical Sciences (CIOMS) form/Extensible Markup Language (XML) file to the LSO/CRO for submission to the competent authorities, IEC/IRBs, and investigators, according to regulations. The investigator is responsible for ensuring that the IEC/IRB is also informed of the event, in accordance with national and local regulations.

Note: Although pregnancy is not a serious adverse event, the process for reporting a pregnancy is the same as that for reporting a serious adverse event, but using the pregnancy form (see Section 7.6).

7.5.5.3.2. Sponsor Responsibility

If a serious unexpected adverse event is believed to be related to the study drug or study procedures, the sponsor will take appropriate steps to notify all investigators participating in sponsored clinical studies of Copaxone and the appropriate competent authorities (and IEC/IRB, as appropriate).

In addition to notifying the investigators and competent authorities (and IEC/IRB, as appropriate), other measures may be required, including:

- altering existing research by modifying the protocol
- discontinuing or suspending the study
- altering the process of informed consent by modifying the existing consent form and informing all study participants of new findings
- modifying listings of expected toxicities to include adverse events newly identified as related to Copaxone

7.5.6. Protocol-Defined Adverse Events for Expedited Reporting

No protocol-defined adverse events for expedited reporting were identified for this study.

7.5.7. Overdose of Study Drug

Any dose of study drug (whether the investigational product, reference treatment, or placebo), whether taken intentionally or unintentionally, in excess of that prescribed must be immediately reported to the sponsor.

7.5.8. Protocol Deviations Because of an Adverse Event

If a patient experiences an adverse event or medical emergency, deviations from the protocol may be allowed on a case-by-case basis. To ensure patient safety, after the event has stabilized or treatment has been administered (or both), the investigator or other physician in attendance must contact the physician identified in the Clinical Study Personnel Contact Information section of this protocol as soon as possible to discuss the situation. The investigator, in consultation with the sponsor, will decide whether the patient should continue to participate in the study.

